6 METHODOLOGY

6.1 Study design

This is a pragmatic, pre- and post-interventional quasi-experimental study combined with a prospective observational study design. The primary aim is to determine the effectiveness of the RITE intervention in increasing the uptake of VMMC at Bwaila STI clinic. The implementation science aim is to determine the potential utility (feasibility, acceptability and appropriateness) of RITE intervention in an STI clinic setting [31]. We will use a sequential mixed methods approach, starting with formative qualitative study to refine the proposed intervention (RITE), followed by a pragmatic, mixed-methods quasi-experimental study with one pre-exposure and four distinct exposure groups [7]. This stand-alone intervention will be implemented at a practical STI clinic setting without random allocation to the intervention. We will observe for the standard of care (SOC) in the pre-intervention phase and introduce our intervention in a step fashion of different intervention combinations with four different intervention groups. This approach will allow us to assess the effect of the intervention while assessing the effect of different combinations of the intervention components, building up to the full intervention. Since the STI clinic is an outpatient clinic and STIs are generally acute infections that resolve quickly with treatment, it is not possible to randomize intervention components and follow the same participants over time as a cohort hence the different exposure groups. The key outcome of interest, VMMC uptake, will be measured at the VMMC facility.

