Feasibility will be measured during implementation for each implementation block because it cannot be measured before exposure to the intervention [36]. A vignette (embedded in the data tools) on the RITE intervention will be read out to respondents to describe the intervention. Data on acceptability, appropriateness and feasibility will be collected using the following methods:

Surveys: For acceptability, we will use the acceptability of intervention measure (AIM), a tool designed by Weiner et al [37], to collect quantitative data for acceptability. The AIM uses Likert scales of four constructs which assess if an intervention is appealing, likeable, welcome and approved. For appropriateness, we will use the intervention appropriateness measure (IAM) to collect quantitative data for appropriateness [37]. The IAM uses a Likert scales of constructs which assess if an intervention is fitting, suitable, applicable, and a good match. For feasibility, we will used the feasibility of intervention measure (FIM) for feasibility Surveys [37]. The FIM uses a Likert scales of constructs which assess if an intervention is implementable, possible, doable, and easy to use. These tools have been slightly modified to suit the study setting.

Acceptability and appropriateness will be conducted at baseline and for each implementation block except for feasibility which cannot be assessed before exposure to the intervention (Appendix 6 - 9). Surveys data will be collected on electronic tablets through open data kit (ODK). Data clerks will administer surveys on an electronic tablet for the men while HCWs will self-administer the surveys. Each survey will to last approximately 10 - 20 minutes. Survey data will be downloaded from the tablets to a Microsoft Access password-locked database. IDIs and FGDs will complement the surveys.

In-depth interviews: IDIs will be conducted with HCWs from Bwaila STI clinic only. IDIs will

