be ideal for HCWs because they are fewer in number, easier to reach and will provide a platform to explore in more detail if our intervention is practical for the clinic. IDIs will be conducted in the local language (Chichewa) by the investigator with the help of a qualitative researcher. We will conduct interviews with HCWs before implementation (baseline) and during implementation (during the last implementation block with the full RITE intervention) to explore implementation issues until saturation is reached. Each interview will last approximately 45 – 60 minutes. IDIs will be administered using an interview guide developed by the investigator in consultation with qualitative researchers are the University of North Carolina Project (UNC Project) in Malawi (Appendix 10).

Focus Group Discussions: FGDs will be conducted with the men only. FGDs will be ideal for the men because they will allow us to collect opinions from more men at one time compared to IDIs. Men will be purposively recruited and segmented by meaningful characteristics, such as age, marital status, religion or other factors that the experts think would influence what and how men may share information. FGDs will be conducted in Chichewa by the investigator with help from qualitative researchers. The FGDs will be administered using a guide developed by the investigator and qualitative researchers from UNC project (Appendix 11). Each FGD will have between 8 to 12 men. We will conduct two FGDs before implementation at baseline (appendix 11) and another two FGDs during implementation of the full RITE intervention only (appendix 11). Each FGD will be approximately 60 – 90 minutes. The IDIs and FGDs will complement the quantitative methods by exploring factors identified in surveys.

We will take notes and record the IDIs and FGDs. IDIs and FGDs will be translated to English during transcription. The investigator and one qualitative researcher will conduct the transcription and coding using Nvivo 14 S.E. in preparation for thematic analysis. We will

ensure intra-coder and inter-coder consistency by comparing codes. In case of inter-coder inconsistencies, a third person (socio-behavioural scientist) will conduct the coding (tiebreaker). We will collect demographic data from all respondents. A summary of methods is available in Table 1, Appendix 12.

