6.3 Sample Size Calculation and Justification

Data on the incidence of VMMC among men with STIs is unavailable. Based on routine data, the Bwaila STI clinic sees about 60 patients per day. Of these, 27 patients are men. Using the prevalence of circumcision from the MoH integrated HIV Program third quarter report of 28% among men with STI, we estimate that at least 19 uncircumcised men will visit the STI clinic per day and at least 380 uncircumcised men per month. Since the project implementation period is expected to be about 6 months, we expect that a minimum of 2280 uncircumcised men will be exposed to our intervention and observed for VMMC uptake.

We will offer all men who express interest in VMMC to participate in a survey. We anticipate between 5-15% of the men will decline participation in the survey. All (approximately 12) healthcare workers will be offered to take the surveys. All available experts (approximately 10) will be offered to take a survey.

Sample size for surveys

Based on the total sample size of 80 men indicated below, we calculated that 67 surveys are required for each intervention component to achieve 95% confidence level with 5% margin of error [38]. We will offer all men who express interest in VMMC to participate in a survey. We anticipate between 5-15% of the men will decline participation in the survey. All (approximately

12) healthcare workers will be offered to take the surveys. All available experts (approximately 10) will be offered to take a survey.

Data Analysis

Overall, we will use descriptive statistics such as mean, median and proportion to describe the demographic characteristics of the study population by implementation block. Demographic characteristics will include but not limited to age, marital status, educational status and socio-economic status. These characteristics will be compared with the SOC group using Student's T-test or Chi-squared test at $\alpha=0.05$ and 95% confidence interval, assuming normal distribution.

Objective 1: To compare uptake of voluntary medical male circumcision between the standard of care and the different combinations of the RITE intervention among men attending Bwaila STI clinic in Lilongwe Malawi

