calculated as a median score and percentages for each of the survey questions. The results will be compared between SOC and each implementation block using Wilcoxon sign-ranked test, analysis of variance (ANOVA) and test of proportions as required. We propose to use structural equation modelling to assess predictors of acceptability, appropriateness and feasibility. The latent variables will be acceptability, appropriateness and feasibility. We assume that the constructs measuring each of these latent variables are correlated, we will conduct principal component analysis and calculate factor loadings and error variance to estimate the true effect of the constructs. We also assume that the latent variables will be correlated. Therefore, we will conduct confirmatory factor analysis to assess how the latent variables will affect the impact of our intervention on uptake of VMMC.

Qualitative data will be analyzed using a thematic approach (thematic framing and coding, indexing, and charting). We will conduct data analysis concurrent with interviews to identify salient themes and areas that may require further exploration in the subsequent interviews. Salient themes will be deduced from codes identified from the IDIs and FGDs.

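### Men in the standard-of-care phase may hear a description of RITE before their uptake is measured, and nothing in the plan keeps them out of the uptake comparator

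*Combined protocol and SAP*

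**What the plan says.** Under 6.1 Study design, SOC is the first, non-randomised phase: "We will observe for the standard of care (SOC) in the pre-intervention phase". The Data Analysis text in 6.3 defines uptake as men circumcised divided by uncircumcised men offered the procedure. It compares each of the four blocks with SOC, for uptake (Objective 1) and for time-to-uptake (Objective 1a). SOC is the only comparator.

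The Objective 3 text in 6.2 Data Collection adds a survey: "Acceptability and appropriateness will be conducted at baseline and for each implementation block". Data clerks administer it to the men, and it lasts 10-20 minutes. On content: "A vignette (embedded in the data tools) on the RITE intervention will be read out to respondents to describe the intervention". The analysis text for the scores reads: "The results will be compared between SOC and each implementation block". On who is approached, 6.3 says: "We will offer all men who express interest in VMMC to participate in a survey". On refusal it says: "We anticipate between 5-15% of the men will decline participation in the survey".

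The table of contents lists four men's survey tools, titled I, IE, ITE and RITE, and no separate baseline tool. The tools themselves are not in the text available. Two focus groups of 8-12 men are also planned at baseline.

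Two provisions bear on prior exposure. The exclusion criterion removes men with earlier research exposure who return for a repeat visit. The limitations section relies on one-week wash-outs between interventions.

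**The concern.** The SOC group should show what happens without the intervention. Comparing survey scores between SOC and the blocks requires survey data from the SOC phase. If those data come from men in the SOC uptake denominator, some of those men hear about services they are not being given, and they are the men most likely to be circumcised.

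The outcome is undergoing the procedure, not expressing interest in it. Under 6.2 Study setting, men with symptomatic STIs are not circumcised on the day of the visit. A survey held at that visit would therefore come before their outcome.

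A man who learns of help that is not yet available might wait, which lowers SOC uptake and lengthens SOC time-to-uptake. A man who has a long conversation about circumcision might be prompted to go, which raises uptake. Analysis could not cleanly undo either effect, because dropping surveyed men would remove mainly the interested ones.

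**Working it through.** **1. The plan's own figures.** The survey size is stated as follows: "Based on the total sample size of 80 men indicated below, we calculated that 67 surveys are required for each intervention component". With p = 0.5, a 5% margin and 95% confidence, n0 = 1.96² × 0.25 / 0.05² = 384.1. With the finite population correction for 80, n = 384.1 / (1 + 383.1/80) = 66.4, rounded up to 67, which reproduces. Accrual also reproduces: 27 × 0.72 = 19.4, taken as 19 per day; 19 × 20 = 380 per month; 380 × 6 = 2280. The plan gives no power or effect size for uptake.

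**2. How many SOC men could be exposed.** The length of the SOC phase is not stated. Assume 3-4 weeks, as for a block, and five clinic days a week: 19 × 5 × 3 = 285 and 19 × 5 × 4 = 380 men. If 67 are surveyed in SOC (an assumption, since 67 is set per intervention component), the share is 67/380 = 18% to 67/285 = 24%. If instead every interested man is offered the survey, 1 − 0.15 = 85% to 1 − 0.05 = 95% of interested men are surveyed.

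**3. Do the written safeguards apply?** The exclusion criterion acts on a return visit, not on a man surveyed at his first visit. The wash-outs separate interventions and cannot remove information given inside the SOC phase. No sensitivity analysis by survey status is planned.

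**4. Which contrasts are affected.**

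| Vignette read | SOC | Blocks one to three | Block four |
|---|---|---|---|
| Full RITE text throughout | hears of unavailable components | also hears of unavailable components | all components available |
| Each block's own components | baseline content not stated | hears only what is offered | all components available |

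With the full text throughout, waiting for reimbursement would occur in SOC and in blocks one to three, so it is largely shared there. It would not be shared with block four. The effect of the survey conversation itself occurs in every phase and largely cancels.

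**5. Illustration only.** Shift in SOC uptake = share interested × share of those surveyed × change in conversion among the surveyed. None of the interest rate, the conversion change or SOC uptake is in the documents. With 10-30% interested, 85-95% surveyed and a change of 10-20 percentage points either way:
- smallest: 0.10 × 0.85 × 0.10 = 0.85 points
- largest: 0.30 × 0.95 × 0.20 = 5.7 points
- middle case: 0.20 × 0.95 × 0.10 = 1.9 points

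For the middle case, take a two-sided 5% test of two proportions with 285-380 men per group and a shift in SOC alone, which is the block-four situation. A 1.9-point fall with no true effect gives a false finding in favour of the block with probability 21-26% at 5% true uptake and 12-15% at 10%, against 2.5% nominal. A 1.9-point rise cuts power for a true 5% versus 11% from 75-86% to 40-51%.

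**The case against.** The strongest reply is that the plan does not say the harmful sequence will happen. Survey timing relative to the procedure is not given, and the men approached have already expressed interest. The Sampling section says survey men are purposively recruited, which sits beside the offer to all interested men and may mean that fewer are exposed. Refusal is allowed, and the denominator is all men offered the procedure, so most SOC men may hear nothing. This stands as a limit on what can be claimed. It does not remove the gap, because the plan contains no rule preventing the sequence and its own score comparison calls for SOC-phase surveys.

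A reader might infer that SOC men are told of a later payment, hold back, and so inflate every block's apparent effect. The documents do not support that. The vignette text is not available, the listed tools are specific to components, and nothing says men are told that reimbursement will start later. The direction could be the opposite. If one text is read throughout, blocks one to three share much of any effect.

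The focus groups are a weaker route. 6.1 Study design places formative qualitative work before the quasi-experiment, and the 16-24 baseline men (2 × 8 to 2 × 12) are not shown to be in the SOC denominator. That needs confirming and is not evidence of contamination.

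**Conclusion.** The concern holds as a missing safeguard on the sole uptake comparator. As written, interested men in the SOC phase may be read a description of RITE before their outcome is measured, and nothing delays the survey or takes them out of the denominator. SOC uptake and time-to-uptake may be affected in either direction, most clearly in the comparison with block four, which is the full intervention.

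This rests on reading the baseline survey as the SOC survey, which the planned score comparison supports. The exposure shares of 18-24% and 85-95% depend on the assumptions in step 2. The bias and error rates in step 5 show only that modest shifts would matter at this sample size; they are not estimates for this study. It is not established that uptake is distorted, that payment is mentioned at baseline, or that all four contrasts are inflated. The point should be settled before SOC enrolment, because the analysis cannot repair it well afterwards.

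**What to change.** Amend the Objective 3 text in 6.2 Data Collection and the survey text in 6.3 as follows:

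- Read no RITE vignette to any man in the SOC uptake denominator before his uptake outcome is recorded.
- Run the baseline men's survey in a calendar window after SOC enrolment closes and before block one. Leave all attenders of that window out of Objectives 1 and 1a, so that exclusion is by date and not by interest.
- State what the baseline vignette contains. In blocks one to three, read only that block's own components.
- Confirm that the men in the baseline focus groups are outside the SOC denominator.

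**Cost.** Baseline scores would come from men adjacent to the SOC cohort, not from the cohort itself. One week yields about 19 × 5 = 95 uncircumcised men. Reaching 67 from interested men alone would need 67/(95 × 0.95) = 74% to 67/(95 × 0.85) = 83% of attenders to be interested. There are three ways round this:

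- Survey all uncircumcised attenders of that week: 95 × 0.85 = 81 to 95 × 0.95 = 90 surveys. Record interest, so that the comparison with the blocks, where respondents are interested men, can allow for it.
- Use a longer window.
- State a smaller baseline number with its wider margin. On the plan's population of 80, for example, 40 surveys give 1.96 × √(0.25/40 × 40/79) = 11 points, against the planned 5.

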6.3 Sample Size Calculation and Justification

Data on the incidence of VMMC among men with STIs is unavailable. Based on routine data, the Bwaila STI clinic sees about 60 patients per day. Of these, 27 patients are men. Using the prevalence of circumcision from the MoH integrated HIV Program third quarter report of 28% among men with STI, we estimate that at least 19 uncircumcised men will visit the STI clinic per day and at least 380 uncircumcised men per month. Since the project implementation period is expected to be about 6 months, we expect that a minimum of 2280 uncircumcised men will be exposed to our intervention and observed for VMMC uptake.

We will offer all men who express interest in VMMC to participate in a survey. We anticipate between 5-15% of the men will decline participation in the survey. All (approximately 12) healthcare workers will be offered to take the surveys. All available experts (approximately 10) will be offered to take a survey.

Sample size for surveys

Based on the total sample size of 80 men indicated below, we calculated that 67 surveys are required for each intervention component to achieve 95% confidence level with 5% margin of error [38]. We will offer all men who express interest in VMMC to participate in a survey. We anticipate between 5-15% of the men will decline participation in the survey. All (approximately

12) healthcare workers will be offered to take the surveys. All available experts (approximately 10) will be offered to take a survey.

Data Analysis

Overall, we will use descriptive statistics such as mean, median and proportion to describe the demographic characteristics of the study population by implementation block. Demographic characteristics will include but not limited to age, marital status, educational status and socio-economic status. These characteristics will be compared with the SOC group using Student's T-test or Chi-squared test at $\alpha=0.05$ and 95% confidence interval, assuming normal distribution.

Objective 1: To compare uptake of voluntary medical male circumcision between the standard of care and the different combinations of the RITE intervention among men attending Bwaila STI clinic in Lilongwe Malawi

Uptake will be calculated as a proportion - the number of men who will undergo VMMC divided by the number of uncircumcised men offered VMMC at the STI clinic. Uptake will be calculated for each implementation block. Uptake for each block will be compared against SOC using Student's T-test at $\alpha=0.05$ significance level and 95% confidence interval, assuming normal distribution.

Objective 1a: To compare time-to-uptake of voluntary medical male circumcision between the standard of care and intervention period among men attending Bwaila STI clinic in Lilongwe Malawi

Time-to-uptake of VMMC will be calculated as the number of days taken for an individual to undergo circumcision at the VMMC clinic from the day they were offered circumcision at the STI clinic. To compare time-to-uptake between SOC and the intervention blocks, we will conduct time-to-event analysis to estimate duration to circumcision and Kaplan Meier curves will be plotted and compared between SOC and implementation blocks. We will also study factors affecting time-to-uptake using cox regression.

Objective 1b: To assess factors affecting uptake of voluntary medical male circumcision among men attending Bwaila STI clinic in Lilongwe Malawi

We will assess factors affecting uptake of VMMC using logistic regression modeling. We will use univariate models to assess association. Covariates with $P<0.05$ and those based on expert knowledge of this topic will be fit into multivariate logistic regression models to control for confounders.

Objective 2: To develop STI clinic setting-specific voluntary medical male circumcision educational material at Bwaila STI clinic in Lilongwe Malawi

We will use thematic analysis approach for qualitative analysis of the consultative meeting notes. The notes will be coded and salient themes will be identified. The content and delivery methods will be deduced from the salient themes.

Objective 3: To assess the acceptability, appropriateness and feasibility of the adaptable RITE intervention among men and healthcare workers at Bwaila STI clinic in Lilongwe, Malawi.

We will use mixed methods to assess acceptability, appropriateness and feasibility. For acceptability, appropriateness and feasibility quantitative surveys, these outcomes will be

calculated as a median score and percentages for each of the survey questions. The results will be compared between SOC and each implementation block using Wilcoxon sign-ranked test, analysis of variance (ANOVA) and test of proportions as required. We propose to use structural equation modelling to assess predictors of acceptability, appropriateness and feasibility. The latent variables will be acceptability, appropriateness and feasibility. We assume that the constructs measuring each of these latent variables are correlated, we will conduct principal component analysis and calculate factor loadings and error variance to estimate the true effect of the constructs. We also assume that the latent variables will be correlated. Therefore, we will conduct confirmatory factor analysis to assess how the latent variables will affect the impact of our intervention on uptake of VMMC.

Qualitative data will be analyzed using a thematic approach (thematic framing and coding, indexing, and charting). We will conduct data analysis concurrent with interviews to identify salient themes and areas that may require further exploration in the subsequent interviews. Salient themes will be deduced from codes identified from the IDIs and FGDs.

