5.4.2 Specific objectives

1. To compare uptake of voluntary medical male circumcision between the RITE intervention and the standard of care among men attending Bwaila STI clinic in Lilongwe Malawi
 - a. To compare time-to-uptake of voluntary medical male circumcision between the RITE intervention and the standard of care among men attending Bwaila STI clinic in Lilongwe Malawi
 - b. To assess factors affecting uptake of voluntary medical male circumcision among men attending Bwaila STI clinic in Lilongwe Malawi
2. To develop STI clinic setting-specific voluntary medical male circumcision educational material at Bwaila STI clinic in Lilongwe Malawi
3. To assess the acceptability, appropriateness and feasibility of the RITE intervention among men and healthcare workers at Bwaila STI clinic in Lilongwe, Malawi.

- a. To assess the acceptability and appropriateness of the RITE intervention among men at Bwaila STI clinic in Lilongwe, Malawi

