6.6.1 Composition

The RITE intervention has been guided by the conceptual framework (figure 1) and Powell et al's refined compilation of implementation strategies [32].

Intensified Health Education (I)

Intensified health education will be more consistent and setting-specific education on VMMC incorporated into the routine STI/HIV health education provided at Bwaila STI clinic.

Currently, health education on VMMC at Bwaila STI clinic is offered once in the morning session – leaving out patients who come later to the clinic. The health education session combines education on HIV and STIs, usually offered by HIV testing counselor or clinic receptionists, and education on medical circumcision, offered by a VMMC mobilizer from the Bwaila VMMC clinic.

In this PhD study, we intend to make health education more setting specific and delivered better by conducting formative research to understand the views of men on VMMC with emphasis on men accessing STI care. In addition, we intend to intensify the education by conducting additional (more than one educational talk as per current standard) educational talks. The health talks will be delivered at Bwaila STI clinic – the recruitment point. The current format of the educational talks will be maintained but in addition, educational material on medical circumcision will be developed based on results from the formative research. The VMMC

mobilizer including the clinic receptionist and counselors will be trained on the educational material. We anticipate that the content of the health talk may involve the following fundamental information: description of VMMC, medical benefits of VMMC and addressing myths and misconceptions around VMMC among other topics. After the group education, men will be asked of their interest in circumcision individually by counsellors (during standard HIV testing) and clinicians as they receive care at the STI clinic.

Clinic Escorts (E)

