6.1 Sampling

We will use purposive sampling to select experts or stakeholders involved in VMMC programs (MoH officials, HCWs and private sector officials) to attend the consultative meeting. Men who will participate in the surveys and focus group discussions will be purposively recruited and segmented by meaningful characteristics, such as age, marital status, religion or other factors that the experts think are vital. We will also use purposive sampling to select healthcare workers (HCWs) to participate in the in-depth interviews (IDIs) and surveys. No sampling techniques will be required for measurement of uptake of VMMC. The sample sizes and time points of measurements have been outlined in the sections below.

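### The men's survey is offered to those interested in VMMC, so acceptability among clinic men may be overstated and block differences may reflect who was surveyed

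*Combined protocol and SAP*

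**What the plan says.** The target population is set in 5.4.2 Specific objectives. Objective 3 is "To assess the acceptability, appropriateness and feasibility of the RITE intervention among men and healthcare workers", and 3a is "To assess the acceptability and appropriateness of the RITE intervention among men at Bwaila STI clinic in Lilongwe, Malawi". Neither is limited to men who want circumcision.

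Two different frames are given for the men's survey:
- 6.3 Sample Size Calculation and Justification states, twice: "We will offer all men who express interest in VMMC to participate in a survey". The only other survey groups named there are healthcare workers and experts.
- 6.1 Sampling states: "Men who will participate in the surveys and focus group discussions will be purposively recruited and segmented by meaningful characteristics".

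On timing, the description of intensified health education in 6.6.1 Composition says: "After the group education, men will be asked of their interest in circumcision individually by counsellors". Under 6.6.2 Implementation, that education starts in block one and continues through every later block.

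On comparison, the Data Analysis text for Objective 3 says: "The results will be compared between SOC and each implementation block using Wilcoxon sign-ranked test". The groups contain different men, because 6.1 Study design says it is not possible to "follow the same participants over time as a cohort hence the different exposure groups".

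6.5 Limitations and anticipated challenges mentions selection bias only for enrolment into blocks and its effect on VMMC uptake, not for the surveys.

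**The concern.** There are two separate problems.

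**Population.** Men who are offered VMMC and show no interest are the men a demand-creation intervention most needs to reach, yet no survey offer to them is described. If they rate RITE lower than interested men do, the survey overstates acceptability and appropriateness for the population named in the objective.

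**Comparability.** Entry to the survey depends on a response given after exposure. If education, escorts, reminders or reimbursement change how many men express interest, they also change who is surveyed. How interest is elicited may differ too. Individual asking by counsellors is described as part of intensified education, while 6.2 Study setting says the clinicians' offer under standard of care is not enforced. A score could then move between standard of care and a block although no man's view has changed.

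What is at stake is the reading of Objective 3: whether the men at this clinic find RITE acceptable and appropriate, and whether adding a component changes that.

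**Working it through.** **1. The plan's own figure.** Inputs from 6.3: a closed group of 80 men, 95% confidence, 5-point margin. A proportion of 0.5 is assumed.
- n0 = 1.96² × 0.25 / 0.05² = 384.15
- n = 384.15 / (1 + 383.15/80) = 66.35, rounded up to **67**

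The stated 67 is reproduced. With 5–15% declining (6.3), 80 men yield 68 to 76 surveys, so 67 is reachable. The calculation is sound for 80 men; the question is which men they are.

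**2. How many men the objective covers.** 6.3 gives 19 uncircumcised men per day, and 6.6.2 gives 3–4 weeks per block. Assuming 5 clinic days a week, this is 19 × 15 = 285 to 19 × 20 = 380 men per block. If the 80 are the interested men in a block, they are 80/380 = 21% to 80/285 = 28% of those attending. That is an inference; the documents give no interest rate.

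**3. Possible overstatement (all rates assumed).** Let q be the share interested, a1 the approval among interested men and a0 the approval among the rest. Approval among all men is q·a1 + (1 − q)·a0, and the overstatement is (1 − q)(a1 − a0). With q = 30% and a1 = 90%:

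| a0 | All men | Survey shows | Overstatement |
|---|---|---|---|
| 80% | 0.27 + 0.56 = 83% | 90% | 7 points |
| 50% | 0.27 + 0.35 = 62% | 90% | 28 points |

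With a1 still 90%, q from 10% to 60% and a0 from 50% to 80%, the range is 4 to 36 points. If a0 equals a1, there is none.

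**4. Possible shift between blocks (all rates assumed, nobody's view changes).** Interest rises from q0 to q1, and newly interested men approve at rate an. The new score is [q0·a1 + (q1 − q0)·an] / q1.
- q0 = 10%, q1 = 20%, a1 = 90%, an = 80%: (0.09 + 0.08)/0.20 = 85%, a fall of 5 points.
- q0 = 10%, q1 = 30%, a1 = 90%, an = 50%: (0.09 + 0.10)/0.30 = 63%, a fall of 27 points.

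With 67 men per group and a two-sided 5% comparison of proportions, the chance of a significant difference is about 14% in the first case and 96% in the second. If newly interested men rated RITE higher than the others, the sign would reverse.

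**5. Precision if the frame is widened.** The margin for 67 surveys is 1.96 × √(0.25/67) × √((N − 67)/(N − 1)).

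| N | Margin with 67 | Surveys for 5 points |
|---|---|---|
| 80 | 4.9 points | 67 |
| 285 | 10.5 points | 164 |
| 380 | 10.9 points | 192 |

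At 30% interest, 67 surveys would contain about 20 interested and 47 uninterested men, with margins of about 22 and 14 points (proportion 0.5, no finite-population correction).

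**The case against.** The strongest defence is that the frame has a reason. Under 6.6.1, escorts serve interested men, SMS reminders serve men with an appointment, and reimbursement goes to men who are circumcised. Three of the four components therefore reach only interested men, and asking recipients what they think is a legitimate choice. Acceptability is also defined as a perception of RITE, not of circumcision, so a man who declines surgery may still find the education or the refund agreeable.

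Both points stand. They mean that a reader who concludes that acceptability is inflated goes further than the documents allow: no interest rate and no ratings by interest are given. A reader might also infer that block four will look less acceptable because reimbursement draws in less enthusiastic men. That is one scenario among several, and the direction is not known.

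The defence does not remove the mismatch with the objective. Education reaches all men, and under 6.2 Data Collection a vignette describing RITE is read to respondents, so uninterested men could answer. Comparing demographics by block would show some changes in case mix, but not differences in interest.

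The word surveys in the Sampling section may be a drafting slip, since 6.2 Data Collection repeats nearly the same sentence for focus groups alone. The survey tools and methods summary are appendices outside the available text, so eligibility stated there cannot be checked.

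**Conclusion.** The point holds as a mismatch between the objective and the survey frame, with possible bias of unknown size. Followed as written, the plan yields respondents selected by interest or by purpose, while Objectives 3 and 3a speak of men at the clinic. Because interest is asked after exposure, differences between standard of care and the blocks may reflect who was surveyed. The 7- and 28-point figures rest entirely on assumed rates and show only how strongly the answer depends on men who are not asked.

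Two further inferences are not supported. The 67 is not miscalculated; it is correct for a closed group of 80. Nor can 67 surveys be moved to a wider frame with the 5-point margin intact, because over 285 to 380 men the margin is about 10.5 to 10.9 points. Purposive recruitment for the focus groups is ordinary practice; the difficulty lies in using it for scores that carry a confidence level and significance tests.

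This should be corrected, but it touches an implementation objective. Uptake is calculated over all uncircumcised men offered VMMC and is not affected.

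**What to change.** First reconcile the two sampling statements by limiting purposive recruitment of men to the focus groups. Then choose one route and state it:

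- **(a) Match the frame to the objective.** Take about 67 surveys per block, consecutively or at a fixed interval, from all uncircumcised men offered VMMC. Record interest, and report results by interest and block. Restate the precision as about 10.5 to 10.9 points (285 to 380 men per block, 5 clinic days a week), and label results by interest as descriptive. Cost: no extra surveys, a wider stated margin, and probably somewhat more refusals. Keeping 5 points would need 164 to 192 surveys per block, about 2.4 to 2.9 times as many.
- **(b) Match the objective to the frame.** Keep the survey for interested men, restrict the Objective 3 conclusion for men to those who expressed interest, and report the numbers offered VMMC, interested and surveyed in each block. Treat comparisons of scores between standard of care and the blocks as descriptive. Cost: a narrower conclusion and little extra work, since numbers offered and referred are already to be collected.

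Route (a) removes selection by interest but not other differences between periods, because blocks are not randomized.
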